11.4.4. Special Reporting Situations

Special Reporting Situations that occur during the study period, as defined in Section 11.2.5, will be reported to Janssen Research & Development on a quarterly basis unless they are serious adverse events. Serious adverse events will be reported using the MedWatch 3500A Form within 24 hours of becoming aware of the event. Safety information to be included in each safety report is summarized in section 11.2.5.

11.4.5.Individual Case Safety Report (ICSR)

All reports of serious adverse events must contain the elements described for Individual Case Safety Reports (ICSR). A valid ICSR must contain the four minimum criteria required to meet regulatory reporting requirements.

Confidential Page 20 of 28

 an identifiable subject (but not disclosing personal information such as the subject's name, initials or address)

- an identifiable reporter (investigational site)
- a Janssen medicinal product
- an adverse event, outcome, or certain special situations

The minimum information required is:

- suspected Janssen medicinal product (doses, indication)
- date of therapy (start and end date, if available)
- batch or lot number, if available
- subject details (subject ID and country)
- gender
- age at AE onset
- reporter ID
- adverse event detail (AE verbatim in English), onset date, relatedness, causality, action taken, outcome, (if available)

11.4.6. Product Quality Complaints (PQC)

A PQC may have an impact on the safety and efficacy of the product. Timely, accurate, and complete reporting and analysis of PQC information from studies are crucial for the protection of patients, investigators, and Janssen Research & Development, and are mandated by regulatory agencies worldwide. Janssen Research & Development has established procedures in conformity with regulatory requirements worldwide to ensure appropriate reporting of PQC information. Lot and/or Batch #s shall be collected or any reports failure of expected pharmacological action (i.e., lack of effect). The product should be quarantined immediately and if possible, take a picture.

All initial PQCs involving a Janssen medicinal product under study must be reported to Janssen Research & Development by the Sponsor Investigator within 24 hours after being made aware of the event. The Janssen contact will provide additional information/form to be completed.

If the defect for a Janssen medicinal product under study is combined with either a serious adverse event or non-serious adverse event, the Sponsor Investigator must report the PQC to Janssen Research & Development according to the serious adverse event reporting timelines. A sample of the suspected product should be maintained for further investigation if requested by Janssen Research & Development.

11.5. Maintenance of Safety Information

All safety data will be maintained on source documents.

12.STATISTICAL METHODS

12.1.Primary Endpoint

We will analyze the change in IL-6-induced p-STAT3 mean fluorescence intensity at each time point in the study. Based on the published pharmacodynamics of Siltuximab, a maximal reduction in p-STAT3 signaling is expected to occur two weeks post-infusion. The correlation of a p-STAT3 response to Siltuximab treatment will be assessed by comparing the mean p-STAT3 Δ MFI at Screening to Baseline () using a paired two-tailed t-test. This represents random biological variability of the measurement over time. We will also compare the mean p-STAT3 Δ MFI at baseline to that at 2 weeks following infusion. This comparison will determine if we can reject the null hypothesis that Siltuximab does not modulate IL-6-dependent p-STAT3.

To determine if Siltuximab induces a durable reduction in p-STAT3, defined as maintenance of a moderated response 12 weeks after infusion, we will compare the mean p-STAT3 Δ MFI at Week 12) to the mean p-STAT3 Δ MFI at Baseline, using a paired 2-tailed t-test.

We will perform additional exploratory analyses to determine what factors correlate with the degree of p-STAT3 modulation by Siltuximab. These factors may include age, duration of disease, HLA type, single nucleotide polymorphisms, measures of glycemic control such as HbA1c, circulating concentration of Siltuximab, and baseline p-STAT3 responses.

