5. STUDY DESIGN

[figure not shown]
5.1.Overview

This trial will be conducted as a single arm, open-label, single-dose, mechanistic endpoint study of Siltuximab in adult subjects diagnosed with type 1 diabetes (T1D). Subjects diagnosed with T1D and meeting eligibility criteria will receive a single intravenous infusions of 11 mg/kg

Confidential Page 8 of 28

Siltuximab. An abbreviated Schedule of Events is provided in Figure 1 to illustrate the study design.

Figure 1. Overview of study assessments.

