6. CRITERIA FOR EVALUATION

6.1.Primary Endpoint

• Change in IL-6 stimulated intracellular p-STAT3 between Week 12 and baseline.

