6.2. Secondary Endpoints

- Change in IL-6 stimulated intracellular p-STAT3 between Week 2 and Baseline.
- Change in IL-6 stimulated intracellular p-STAT3 between Week 2 and Week 12.
- Sensitivity of effector T cells to suppression by regulatory T cells
- Frequency of effector T cells secreting IL-17 and other cytokines
- Correlation of circulating Siltuximab concentration to p-STAT3 response

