10.1. Clinical Assessments

A schedule of procedures is provided in Attachment 1. Descriptions of all assessments are described in subsequent sections.

10.1.1.General Assessments

- Informed consent: written informed consent will be obtained from the participant before any study assessments or procedures are performed;
- Eligibility criteria: eligibility for study participation will be assessed during the screening period;
- Medical History: Relevant medical history, including history of current and previous disease, and review of systems will be obtained. Adverse events will be assessed. A directed physical exam-will be conducted as indicated by medical history;
- Concomitant medications: concomitant medications and their indications will be recorded;
- Vital Signs: Body temperature, blood pressure, pulse and respirations will be measured at Screening (Visit 1) and Baseline (Visit 2).

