10.3. Mechanistic Assessments

10.3.1.IL-6 Induced p-STAT3

The primary objective of this study is to determine whether Siltuximab can durably suppress the phospho-STAT3 (p-STAT3) response to IL-6. The methods used to assess p-STAT3 may change as new assay become available, but are currently expected to be as follows. PBMC will be incubated with recombinant human IL-6 and then analyzed by flow cytometry after intracellular staining with a p-STAT3-specific antibody. The degree of STAT3 phosphorylation will be determined both before and after IL-6 stimulation. The change in phosphorylation levels will be quantified for each sample and will be compared before and after Siltuximab exposure. As the primary endpoint, we will determine whether the induction of p-STAT3 by IL-6 is significantly reduced at Week 12 compared to baseline.

Confidential Page 14 of 28

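### Section 12.1 misdescribes the Screening-versus-Baseline t-test: it can show neither response to Siltuximab nor the size of random variability. Reword it as a drift check and report the within-subject SD.

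*Combined protocol and SAP*

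**What the plan says.** Section 12.1 introduces the first comparison with "The correlation of a p-STAT3 response to Siltuximab treatment will be assessed by comparing the mean p-STAT3" ΔMFI at Screening with that at Baseline, using a paired two-tailed t-test. The next sentence interprets it: "This represents random biological variability of the measurement over time".

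The section then adds a comparison of Baseline with Week 2, of which it says "This comparison will determine if we can reject the null hypothesis" of no modulation by Siltuximab. The durable effect is tested by Week 12 against Baseline, again with a paired two-tailed t-test.

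The endpoint sections agree with those last two comparisons. Section 6.1 gives "Change in IL-6 stimulated intracellular p-STAT3 between Week 12 and baseline" as primary, and Section 6.2 includes "Change in IL-6 stimulated intracellular p-STAT3 between Week 2 and Baseline" as secondary. Section 10.3.1 repeats the primary comparison: "we will determine whether the induction of p-STAT3 by IL-6 is significantly reduced at Week 12 compared to baseline". Screening appears in none of them.

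Section 10.1.1 labels Visit 1 as Screening and Visit 2 as Baseline. Attachment 1 puts them at Day -14 (window +/- 7) and Day 0, with mechanistic assays marked at both. Neither Section 12.1 nor Section 12.2 commits to reporting a within-subject SD, an SD of differences or a correlation.

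**The concern.** The two sentences give one contrast two incompatible roles, response to treatment and noise without treatment, and the chosen test fits neither.

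- **Drug response.** Two samples taken before the infusion carry no information on what the infusion does.
- **Random variability.** A paired t-test asks whether the mean of the differences is zero. Random variability sits in the spread of the differences, which the test uses only as a yardstick. The p-value does not reveal how large that spread is.

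This would be a small slip in a controlled trial. Here Section 5.1 says: "This trial will be conducted as a single arm, open-label, single-dose, mechanistic endpoint study of Siltuximab". With no untreated arm, the two early samples are the only planned comparison of p-STAT3 in these subjects without drug. If they are summarised by a p-value, a non-significant result from 10 subjects could be taken to show a stable measurement, which it would not show. The variability that the section names would also go unreported.

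**Working it through.** **Inputs.** Section 12.2 gives mean ΔMFI 3.2, SD 1.3, two-tailed α 0.05 (sidedness from Section 12.1), power 0.8, a 50% reduction as the planned effect (0.5 × 3.2 = 1.6), and 10 evaluable subjects. The documents do not give the correlation ρ between two samples from one subject, so it is assumed and varied. The SD of 1.3 is read as the SD across patients and taken as equal at both visits.

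**The plan's own figure.** SD of paired differences = 1.3 × √(2(1 − ρ)). With exact noncentral-t power for a difference of 1.6, the stated 9 subjects is the minimum only when ρ is about 0.33 to 0.43 (SD of differences about 1.50 to 1.38). At ρ = 0 the requirement is 13, and at ρ = 0.5 it is 8. The stated 9 is therefore reproducible, but under a correlation that is not written down. The value 0.33 below is the lower end of that range; 0.6 and 0.9 represent a more repeatable assay.

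**Step 1: does the test result reflect random variability?** Simulate the Screening-Baseline t-test with n = 10, no drift, and 200,000 trials per setting:

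| Within-subject SD | Rejection rate |
|---|---|
| 0.2 | 5.00% |
| 0.5 | 4.96% |
| 1 | 5.05% |
| 1.06 | 5.03% |
| 3 | 5.01% |

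A valid 5% test must behave this way, which is the point: its result does not change with the quantity it is said to represent. In a separate run over SDs from 0.1 to 2.0, the median p-value stayed near 0.50 throughout. The SD of the differences divided by √2 did follow the truth (mean estimate 0.097 at a true 0.1, and 1.95 at 2.0).

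**Step 2: what can the comparison say about drift?** With n = 10 (9 df):

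- 95% CI half-width of the mean difference = 2.262 × SD of differences / √10.
- Drift detectable with 80% power = 0.996 × SD of differences (noncentral t).
- Miss probability = chance of p > 0.05 when the true drift is 0.8, half the planned 1.6.

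| Assumed ρ | SD of differences | CI half-width | Detectable drift (% of 3.2) | Drift of 0.8 missed |
|---|---|---|---|---|
| 0.33 | 1.505 | 1.08 | 1.50 (47%) | 68% |
| 0.6 | 1.163 | 0.83 | 1.16 (36%) | 51% |
| 0.9 | 0.581 | 0.42 | 0.58 (18%) | 3% |

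For example, at ρ = 0.33 the half-width is 2.262 × 1.505 / 3.162 = 1.08. Simulation (200,000 trials each) gave miss rates of 67.5%, 50.8% and 2.9%.

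**Step 3: what would the missing estimate look like?** Within-subject SD = SD of differences / √2. Its 95% CI runs from √(9/19.02) = 0.69 to √(9/2.70) = 1.83 times the estimate.

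| Assumed ρ | Within-subject SD | 95% CI if that value is observed |
|---|---|---|
| 0.33 | 1.06 | 0.73 to 1.94 |
| 0.6 | 0.82 | 0.57 to 1.50 |
| 0.9 | 0.41 | 0.28 to 0.75 |

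The estimate is imprecise, so it should not appear without its interval.

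**The case against.** The strongest reply is that Section 12.1, read as a whole, already does most of what is asked. It calls Screening versus Baseline random variability, then gives the test of drug effect to Week 2 and the durable effect to Week 12. On that reading, the fault is one careless lead-in clause in a sentence that contains an empty pair of parentheses where text may have been lost. The comparison feeds no decision rule. The SD of the differences is computed in running the test, and nothing says that only a p-value will be reported. The protocol never says that it will read non-significance as stability. The drift figures depend on assumed correlations and range widely. The proposed SD would be imprecise and would cover a much shorter interval than the primary endpoint.

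Much of this stands. The treatment inference is correctly placed, the empty parentheses are not counted as an error, and the consequence is limited. Two points survive even the charitable reading. A t-test of means is still the wrong summary of random variability, and the plan does not commit to reporting the SD that would be the right one. The wide range of the drift figures is itself a reason to report an estimate with an interval: at the two lower correlations, a non-significant result reassures very little.

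The pre-dose timing of the Day 0 sample is an inference, because the schedule has no infusion row and does not order the sample against the infusion. The protocol's own description of the comparison as random variability supports it. If the sample were taken after dosing, that description would fail for a different reason.

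**Conclusion.** The concern holds. As written, the Screening-Baseline t-test suits neither of its stated purposes. It cannot show a response to Siltuximab if Baseline is the pre-dose Day 0 sample, and its result does not reflect the size of random variability under any assumption about correlation.

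The consequence is limited to one auxiliary comparison. The primary Week 12 test, the Week 2 test, α and the sample size are unaffected. What is at stake is how well a single-arm change can be interpreted. The miss rates of 68%, 51% and 3% for a drift of 0.8 rest on an SD of 1.3 at both visits and on assumed correlations of 0.33, 0.6 and 0.9. The conclusion about the test does not depend on them. This should be corrected, but it does not threaten the primary analysis.

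**What to change.** In Section 12.1:

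1. Describe Screening versus Baseline as a check for drift before treatment. Report the mean difference with its 95% CI. State that inference about Siltuximab rests on Week 2 versus Baseline and Week 12 versus Baseline.
2. Replace the sentence on random variability with a commitment to estimate the within-subject SD, as the SD of the Screening-Baseline differences divided by √2, with its 95% CI.
3. State the limits of that estimate. It includes assay variation, and it covers 7 to 21 days (Day -14, window +/- 7), not the 84 days to Week 12, so it may understate variability over the primary interval.
4. State that Baseline is the Day 0 sample taken before the infusion, if that is so.

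The within-subject SD would also let readers examine, imprecisely, the correlation implied by the 9 subjects in Section 12.2.

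The cost is a wording amendment with the IRB approval that Section 14.3 requires, plus one descriptive estimate. Attachment 1 already schedules mechanistic assays at both visits, so no visit, assay, endpoint or test changes. The edit can travel with another amendment.

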12.2. Sample Size Rationale

Based on previous studies, the mean IL-6 induced p-STAT3 Δ MFI in T1D patients is 3.2 with a standard deviation of 1.3. Assuming a similar standard deviation before and after treatment, an α of 0.05 and power (1- β) of 0.8, the number of subjects required to detect a 50% reduction in the mean p-STAT3 Δ MFI using a paired t-test is 9 subjects. We propose enrollment of 10 subjects with evaluable data in order to ensure at least this level of power.

13.DATA COLLECTION, MONITORING, AND SAMPLE RETENTION

13.1.Data Collection Instruments

The Sponsor Investigator will prepare and maintain adequate and accurate source documents designed to record all observations and other pertinent data for each subject treated with the study drug. Data from source documents will be entered into a clinical database. The Sponsor Investigator is responsible for all information collected on subjects enrolled in this study.

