2. PROTOCOL SYNOPSIS

Title .	Modulation of STAT3 Signaling with Siltuximab in Type 1 Diabetes			
Protocol Number	EMU-002			
Short Title	STAT3 Modulation with Siltuximab			
Sponsor Investigator	[name]			
Conducted at	Benaroya Research Institute at Virginia Mason Clinical Research Center [name]			
Funding Organization	Janssen Research &Development, LLC.			
Accrual Objective	10 subjects			
Test Product and Route of Administration	Commercially sourced Siltuximab (100 mg lyophilized powder in single-use vial for intravenous infusion)(SYLVANT™)			
Study Design	This trial is a single arm, open-label, single-dose, mechanistic endpoint clinical study of Siltuximab in adult subjects diagnosed with type 1 diabetes (T1D). Eligible subjects will receive a single intravenous infusion of 11 mg/kg Siltuximab with blood samples for primary outcome obtained 12 weeks later.			
Primary Objective	To determine whether Siltuximab can durably suppress the p-STAT3 response to IL-6.			
Primary Endpoints	Change in IL-6 stimulated intracellular p-STAT3 between Week 12 and baseline			
Secondary Endpoints	 Change in IL-6 stimulated intracellular pSTAT-3 between Week 2 (post-treatment) and baseline. Change in IL-6 stimulated intracellular p-STAT3 between Week 2 (post-treatment) and Week 12. Sensitivity of effector T cells to suppression by regulatory T cells Frequency of effector T cells secreting IL-17 and other cytokines Correlation of circulating levels of Siltuximab to the p-STAT3 response 			
Safety Endpoints	Adverse events associated with Siltuximab treatment			
Major InclusionCriteria	●M/F 18-45 years of age, inclusive ●Diagnosis of T1D within 10 years of enrollment			

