14.5. Withdrawal of Subjects from the Study

A subject may be withdrawn from the study at any time if the subject or the Investigator feels that it is not in the subject's best interest to continue. All subjects are free to withdraw from participation at any time, for any reason, specified or unspecified, and without prejudice. Reasonable attempts will be made by the Sponsor Investigator to provide a reason for subject withdrawals. The reason for the subject's withdrawal from the study will be specified in the subject's source documents.

Individuals without evaluable mechanistic data may be replaced.

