ATTACHMENT 1. Schedule of Events

Table 1. Study Procedures						
Visit Number	1	2	3	4	5	6
Time Point (Day)	-14	0	1.	14 ^b	28 ^b	84 ^b
Visit Window (Day)	+/- 7	-	-	+/- 3	+/- 3	+/- 7
General Assessments	Х	Х	Х	Х	х	Х
Vital Signs	Х	Х	Х			
Islet Autoantibodies	Х					
MMTT ^a	Х					
HbA1c	Х					
HIV, HBV, HCV serology	Х					
QuantiFERON TB test	Х					
EBV, CMV Serology	Х					
EBV, CMV viral load	Х					
Urine Pregnancy Test	Х	Х				
Comprehensive chemistry panel	Х	Х	Х	Х	Х	Х
Lipid Panel	Х	Х	Х	Х	Х	Х
C-reactive Protein	Х	Х	Х	Х	Х	Х
Direct bilirubin	Х	Х	Х	х	Х	Х
Erythrocyte sedimentation rate	Х	Х	Х	Х	Х	Х
CBC	Х	Х	Х	х	Х	Х
HLA Typing and SNP Analysis	Х					
Mechanistic Assays	Х	Х	Х	Х	Х	Х
Pharmacokinetic Samples	Х	Х	Х	Х	Х	Х

^a if not performed within 60 days of study screening visit

^b blood draw Visits 4-6 may be conducted remotely

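### Does an undefined evaluable subject, with replacement left optional, undercut the 80% power that section 12.2 claims for 10 subjects?

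*Combined protocol and SAP*

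**What the plan says.** Section 12.2 takes a mean ΔMFI of 3.2 with SD 1.3, assumes a similar SD after treatment, and works with "an α of 0.05 and power (1- β) of 0.8". The number it reports for detecting a 50% reduction "using a paired t-test is 9 subjects". It then sets the target: "We propose enrollment of 10 subjects with evaluable data in order to ensure at least this level of power".

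Section 12.1 compares Week 12 with Baseline "using a paired 2-tailed t-test", so only subjects with both values enter the primary test. Section 10.3.1 says of the primary endpoint that "we will determine whether the induction of p-STAT3 by IL-6 is significantly reduced at Week 12 compared to baseline".

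The only replacement rule is the last line of section 14.5: "Individuals without evaluable mechanistic data may be replaced". The synopsis gives an accrual objective of 10 subjects and describes the single infusion "with blood samples for primary outcome obtained 12 weeks later". The Attachment 1 row "Mechanistic Assays" is marked at all six visits. Its footnote b lets the blood draws at Visits 4 to 6 be done remotely, and Week 12 has a window of ±7 days.

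**The concern.** The margin over the requirement is one subject. The word that protects it, evaluable, appears only in sections 12.2 and 14.5 and is defined in neither. Section 14.5 says may, not will, and names neither p-STAT3 nor Week 12. A subject sampled through Day 28 and then lost has given samples for mechanistic assays but has no primary-endpoint pair. On a literal reading, 14.5 might not reach that subject. The synopsis figure of 10 could also be taken as a ceiling on enrolment.

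On that reading, nothing operative backs the power promise in 12.2. Two unreplaced losses leave 8 pairs, and because the endpoint is judged by significance, lost pairs turn into missed effects. The trial is also open-label, so a late decision on who is evaluable or replaced could in principle be made with the p-STAT3 values in view.

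**Working it through.** **Inputs.** From section 12.2: mean 3.2, SD 1.3 before and after, 50% reduction, α 0.05, power 0.80, requirement 9, target 10. From section 12.1: two-tailed paired t-test. The documents give neither the within-subject correlation ρ nor a loss rate, so both are shown as ranges.

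**Step 1: reproduce the 9.** The difference to detect is 0.5 × 3.2 = 1.6. The SD of the difference is 1.3 × √(2(1 − ρ)). Power comes from the noncentral t distribution with n − 1 degrees of freedom and noncentrality 1.6 × √n / SD of the difference.

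- At ρ = 0.5 the SD of the difference is 1.3 and the smallest sufficient n is 8.
- The smallest sufficient n is exactly 9 when the SD of the difference lies above 1.384 and up to 1.500, that is ρ from about 0.33 to 0.43.

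The 9 is therefore attainable under an ordinary correlation.

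**Step 2: power by number of pairs.**

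| Pairs | SD of difference 1.500 | 1.384 | 1.3 |
|---|---|---|---|
| 10 | 85.0% | 90.1% | 93.2% |
| 9 | 80.0% | 85.8% | 89.7% |
| 8 | 73.6% | 80.0% | 84.6% |
| 7 | 65.5% | 72.3% | 77.4% |

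One lost pair leaves 9 and meets the requirement. Two leave 10 − 2 = 8. Over the SDs that give exactly 9, power at 8 pairs falls below 80% by between 0 and 80.0 − 73.6 = 6.4 points. At an SD of 1.3 it does not fall below 80% at all.

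**Step 3: how often two or more would be lost, if nobody were replaced.** With an assumed loss probability p per subject, the chance is 1 − (1 − p)^10 − 10p(1 − p)^9. Average power is taken over the binomial number of pairs, for SDs of the difference 1.500 and 1.384.

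| Assumed p | P(fewer than 9 pairs) | Average power |
|---|---|---|
| 5% | 8.6% | 82.4% to 87.8% |
| 10% | 26.4% | 79.4% to 85.1% |
| 15% | 45.6% | 76.0% to 82.0% |
| 20% | 62.4% | 72.3% to 78.5% |

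**Step 4: does the text lead to this case?** Section 12.2 does not plan 10 enrolled less losses. It plans 10 with evaluable data, in a paragraph that concerns only the paired p-STAT3 comparison, so the natural meaning is evaluable for that comparison. With two Week 12 values missing and nobody replaced, the target in 12.2 has not been met.

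The literal reading of 14.5 also defeats itself. Attachment 1 schedules mechanistic samples at Visit 1 and at the Day 0 visit. If any mechanistic sample were enough, almost every enrolled subject would qualify and the replacement sentence would have nearly nothing to act on. IL-6-induced p-STAT3 is the first assay under section 10.3, Mechanistic Assessments, which is also where the Week 12 primary endpoint is stated. The phrase in 14.5 therefore plausibly includes it.

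**The case for a change.** The best case for a change is that a natural reading is not a written rule. Even if evaluable means a complete pair, may does not oblige anyone to replace a lost subject, and the synopsis line carries no qualifier. With so few subjects each pair counts, and a definition fixed without reference to the size of the values would remove any suspicion of selective replacement. Writing it down would take a few sentences.

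It is true that the term is undefined and replacement optional, and a definition would do no harm. The rest is weaker:

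- Making replacement mandatory until 10 pairs exist is not free. The expected number of extra subjects dosed is 10p/(1 − p), or 0.53 at 5% loss and 2.5 at 20%. It would also require a further subject when 9 pairs, the plan's own requirement, are already in hand. Leaving this to discretion is a fair trade-off.
- The higher loss rates in Step 3 are assumptions. A single infusion, remote draws at Visits 4 to 6 and the ±7 day window all work against losing the Week 12 sample.
- The selection worry is possible but has no support in the text. The endpoint is a flow-cytometry reading, and nothing in the documents suggests replacement guided by results.
- Power can be much lower if ρ is small: at ρ = 0 it is 56.3% with 8 pairs. But it is only 68.9% with 10 complete pairs, so that loss comes from the unstated correlation, a separate matter that no definition of evaluable would settle.

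**Conclusion.** The concern does not call for a change. Followed as written, 12.2 yields 10 usable Baseline and Week 12 pairs, with 85% to 90% power where 9 is the exact answer. The shortfall needs three things together: at least two missing Week 12 values, no replacement, and a target in 12.2 left unmet. With 8 pairs the cost is then at most about 6 points of power over that range, and nothing below 80% if the SD of the difference is 1.3. At assumed losses of 5% to 10% with no replacement, average power stays at about 80% or above.

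This rests on reading evaluable as evaluable for the paired test, on the SD of 1.3 in 12.2, and on a correlation near the values that produce the stated 9. What is missing is a definition that any analyst would supply from the test itself. No figure in the plan is shown to be wrong, and the test, the visits and the target would all stay as they are.
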